11 SECONDARY OBJECTIVE: ADVERSE EVENTS (AE)

The third secondary objective is to assess the safety and tolerability of standard RT and TMZ in combination with BMX-001 compared to standard RT and TMZ alone in newly diagnosed HGG patients. The collection of adverse events was stopped 30 days after completion of chemoradiation treatment +/- BMX-001. Adverse events were coded by clinical center staff.

11.1 ENDPOINTS

The phase 2 portion of this study has two adverse event endpoints:

(1) The proportion of patients who experience any grade 3 or 4 adverse event during radiation and temozolomide treatment, and

(2) The proportion of patients who experience a grade 3 or 4 adverse event that is definitely, possibly, or probably related to BMX-001 treatment during this same period.

Adverse events occurring between baseline through 2 weeks after discontinuation of radiation will be the focus of these analyses and will be summarized.

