#### 13.4.1 Phase 2 - Criteria for holding BMX-001

#### Non-Hematologic Criteria

- The occurrence of non-hematologic grade 3 or greater adverse events considered to be possibly, probably, or definitely related to BMX-001 during treatment with BMX-001, excluding grade ≥ 3 alopecia and elevation in alkaline phosphatase, grade ≥ 3 nausea or vomiting unless occurring despite the use of standard anti-emetics; and grade ≥ 3 hypertriglyceridemia or hypercholesterolemia unless occurring despite standard lipid lowering agents.
- 2. Intolerable  $\geq$  Grade 2 Injection Site Reactions
- 3.  $\geq$  Grade 2 electrocardiogram prolonged QTc interval

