## 13.5 End of Study

The end of study for a subject will occur when the subject comes off study for the following reasons: completion of all study tests/procedures, progressive disease, unacceptable toxicity, allergic reaction to TMZ, allergic reactions to BMX-001, non-compliance with study follow-up, or withdrawal of consent. Patient death due to progressive disease will not be reported as a SAE. It is the intent that all patients will be followed as long as possible for survival. See Section 13.7.2 for follow-up requirements after the patient comes off study.

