# 14.1 Adverse Events

An adverse event (AE) is any untoward medical occurrence in a study subject which does not necessarily have a causal relationship with this treatment. For this protocol, the definition of AE also includes worsening of any pre-existing medical condition. An AE can therefore be any unfavorable and unintended or worsening sign (including an abnormal laboratory finding), symptom, or disease that occurs in any subject enrolled in this clinical trial. It may or may not be related to use of the BMX-001. Abnormal laboratory findings without clinical significance (based on the Principal Investigator's judgment) should not be recorded as AEs. But laboratory value changes that require therapy or adjustment in prior therapy are considered adverse events.

From the time the subject signs the informed consent form through 30 days after completion of the final BMX-001 treatment (for subjects in Arm A, this will be 30 days after the last chemo/RT for subjects in Arm B), all AEs must be recorded in the subject medical record and adverse events case report form.

AEs will be assessed according to the CTCAE version 4.03. If CTCAE grading does not exist for an AE, the severity of the AE will be graded as mild (1), moderate (2), severe (3), life-threatening (4), or fatal (5).

Attribution of AEs will be indicated as follows:

- Definite: The AE is clearly related to the BMX-001
- Probably: The AE is likely related to the BMX-001
- Possible: The AE may be related to the BMX-001
- Unlikely: The AE is doubtfully related to the BMX-001
- Unrelated: The AE is clearly NOT related to the BMX-001

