#### 16.5.2.3 Secondary Objective #3 for Phase 2: Adverse Events

The phase 2 portion of this study has two adverse event endpoints: (1) The proportion of patients who experience any grade 3 or 4 adverse event during radiation and temozolomide treatment, and (2) The proportion of patients who experience a grade 3 or 4 adverse event that is definitely, possibly, or probably related to BMX-001 treatment during this same period. Adverse events occurring between baseline through 2 weeks after discontinuation of radiation will be the focus of these analyses.

Adverse Event Monitoring and Tabulations: Adverse events will be tabulated in a different manner for semi-annual reports to the DSMB-Plus / DSMB, the manuscript summarizing the results of this study, and the final report included within ClinicalTrials.gov.

*DSMB-Plus / DSMB Monitoring:* Two tabulations of adverse events occurring during concurrent chemoradiation will be generated for DSMB-Plus / DSMB review including one that includes all toxicities regardless of attribution, and another that includes only toxicities that are possibly, probably, and definitely related to BMX-001 treatment. For each of these tabulations, the maximum grade of each type of toxicity experienced by each patient will be summarized with frequency distributions within each treatment group. The period of observation that will be the focus of these tabulations will extend 2 weeks after termination of radiation treatment. Additional tabulations will summarize adverse events experienced during adjuvant treatment.

For the manuscript, similar summaries of adverse events will be generated.

For ClinicalTrials.gov, serious adverse events and other adverse events will be summarized separately. These tabulations will reflect the number of patients who experience each type of toxicity regardless of grade or attribution.

16.5.2.4 **Secondary Objective #4 for Phase 2: Progression-Free Survival** Progression-Free Survival (PFS) is defined as the time between initiation of protocol treatment and disease progression or death. If the patient remains alive without disease progression, then PFS will be censored at last follow-up. Analyses similar to those described for OS will be generated for PFS.

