10.3.2 REVISED POWER ANALYSIS

For this endpoint to have relevance, a patients must have received some treatment with temozolomide and radiation in either Arm A or B. At this point, analyses suggest that 78 patients in Arm A and 71 patients in Arm B received protocol treatment. With 78 and 71 patients in Arms A and B, respectively, there is 80% power with a one-tailed chi-square test (α =0.05) to detect a reduction in grade 3 or 4 thrombocytopenia from 15% in Arm B (without BMX-001) to 3.7% in Arm A (with BMX-001).

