19 DESCRIPTION OF TABLES FOR REPORTING

The following tables and figures will be produced, source data listings will be provided

Description	Population		
Summary of Subject Disposition	ITT, Safety, Treated		
Summary of Important Protocol Deviations*	Safety		
DEMOGRAPHICS			
Summary of Demographic Characteristics	ITT, Treated		
SAFETY DATA	1		
Summary of All AEs	Safety		
Summary of TEAEs	Safety		
Summary of BMX-001 Related TEAEs	Safety		
Summary of Baseline AEs	Safety		
Summary of all AEs	Safety		
Summary of SAEs/Deaths	Safety		
Narratives of SAEs	Safety		
Summary of Pre and Post dosing Vital Signs	Safety		
Listing of Abnormal ECG findings post BMX-001 treatment	Safety		
Summary of clinically significant:	Safety		
 Clinical Laboratory Evaluations Physical Examinations: Abnormal physical examination findings 	Safety		
PK*	PK		
OUTCOMES			
os	ITT, Treated		
PFS	ITT, Treated		
Thrombocytopenia	ITT, Treated		
Cognitive Testing	ITT, Treated		
HRQoLs	ITT, Treated		
OTHER			
Treatment Disposition: TMZ, RT, BMX-001	Safety		

Treatment Exposure: TMZ, RT, BMX-001	Safety
Concomitant Medications	Treated
Analysis Sets, including subjects excluded from analysis	All
List of Withdrawals	All

^{*=} BioMimetix will provide

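### Both adverse event endpoints stop at grade 4, so a patient whose only severe event is fatal counts as having had no severe event

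*SAP*

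**What the plan says.** SAP 11.1 gives two adverse event endpoints. The first is "The proportion of patients who experience any grade 3 or 4 adverse event during radiation and temozolomide treatment". The second counts events of the same two grades judged definitely, possibly or probably related to BMX-001. Protocol Table 2 (Section 8) and Protocol 16.5.2.3 use the same grades.

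The trial treats fatal as a grade of its own. Where CTCAE offers no grading, Protocol 14.1 supplies a scale whose upper part is "severe (3), life-threatening (4), or fatal (5". Protocol 13.4.1, the rule for holding BMX-001 in Phase 2, has no upper limit: "non-hematologic grade 3 or greater adverse events considered to be possibly, probably, or definitely related to BMX-001".

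On timing, SAP 11.1 adds: "Adverse events occurring between baseline through 2 weeks after discontinuation of radiation will be the focus of these analyses". The window therefore runs past the radiation and temozolomide period named in the first endpoint.

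Deaths have their own outputs. SAP 11.2.2 plans an SAE summary with narratives, and SAP 19 lists a "Summary of SAEs/Deaths" in the Safety population.

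**The concern.** A proportion meant to describe severe toxicity should not fall because an event was fatal. As worded, it does so whenever the fatal event is the patient's only severe one, in either arm.

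The endpoint line also carries some weight of its own. The other adverse event summaries in SAP section 11 are organised by system organ class and preferred term, without a grade breakdown. The two endpoint proportions are therefore the only adverse event outputs in that section defined by grade. A reader of that line would not see that grade 5 is left out, and would have to match it to the deaths table to find out.

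The window raises a lesser question. In the two weeks after radiation Arm A usually still attends for BMX-001, while Arm B has no study visit in weeks 7 and 8. A difference arising late in the window could reflect contact as well as toxicity.

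**Working it through.** **Effect of the grade limit**

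The plan states no expected rate, test, significance level or power for these endpoints, so there is no figure of its own to reproduce. The only treated counts come from the thrombocytopenia section, SAP 10.3.2: "78 patients in Arm A and 71 patients in Arm B received protocol treatment". The population for the adverse event summaries (SAP 11.2.1) is the Safety population, defined in SAP 6 as at least one dose of BMX-001 or temozolomide. I assume it is close to 78 and 71.

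Change in an arm's proportion = (patients whose only severe event is fatal) / (patients in the arm).

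- One patient: 1/78 = 1.28 points in Arm A; 1/71 = 1.41 points in Arm B.
- Two patients: 2/78 = 2.56 points; 2/71 = 2.82 points.

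For scale only, the standard error of the between-arm difference is sqrt(p(1−p)(1/78 + 1/71)). The documents do not give p. At an assumed p of 20% it is 6.56 points, and at 50% it is 8.20 points. One patient is then between 1.28/8.20 = 0.16 and 1.41/6.56 = 0.21 of a standard error.

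**Contact in the two weeks after radiation**

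- Protocol 9.1.5 plans 17 BMX-001 doses: 1 loading + 8 weeks × 2 = 17, which reproduces.
- SAP 6 equates 6 weeks with 13 doses: 1 + 6 × 2 = 13, which reproduces.
- That leaves 17 − 13 = 4 doses for weeks 7 and 8.

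I then listed the possible calendars, assuming 5 fractions a week, no interruptions or missed doses, and Monday/Thursday or Tuesday/Friday injections (a pattern stated in the Phase 1 text, Protocol 9.1.1.1).

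- Radiation starting on a Monday: 3 or 4 doses in weeks 7-8 for both 30 and 33 fractions.
- Exact 14 days after the last fraction, same start: 3 or 4 doses with 30 fractions, 2 to 4 with 33.
- Other start days with 31 to 33 fractions can also give 2 doses in those 14 days, and a single extreme calendar gives 1.

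Arm B has no study visit in weeks 7-8 (Protocol Table 4, footnote q; Protocol 13.3). Other passages still provide contact without an arm limit: weekly blood counts and chemistry through week 8 (Table 4, footnote d; Protocol 9.1.7) and an examination two weeks after radiation and temozolomide (Protocol 13.8.2). After a six-week course that examination falls at the end of week 8. These passages do not fit together as written.

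**The case against.** The strongest reply is that nothing is concealed. Grades 3 and 4 are used consistently in all three places, so this is a stable prespecified definition. Deaths are summarised, SAEs have narratives, all adverse events are listed, treatment-emergent events are tabulated without a grade limit, and death is the primary endpoint. The wording in Protocol 13.4.1 belongs to a dose-holding rule with a different purpose. The count may also be nil. The only related events of grade 3 or above in Phase 1 were one grade 3 tachycardia and one grade 3 hypotension (Protocol 9.2), and Protocol 13.5 says "Patient death due to progressive disease will not be reported as a SAE". A patient with a separate grade 3 or 4 event is still counted. All of this stands, and it limits the point to the endpoint proportion. It does not make that proportion correct when a fatal-only patient exists.

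Three stronger readings are tempting, and the documents do not support them.

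- *An event that worsens from grade 3 to fatal also drops out.* Protocol 16.5.2.3 says that "the maximum grade of each type of toxicity experienced by each patient will be summarized with frequency distributions within each treatment group", but it plans this for monitoring reports and similar manuscript summaries. No passage derives the endpoint from those tables.
- *Arm B's late severe events are lost.* Contact is unequal, but loss is not shown. Besides the examination and blood tests above, adverse events in Arm B are recorded until 30 days after the last chemoradiation (Protocol 14.1), so an event may be recorded late rather than missed. Any loss would make BMX-001 look more toxic, not safer. The related-event endpoint is untouched, since SAP 11.2.3 confines such events to Arm A.
- *Platelet counts are observed unequally.* They are scheduled in both documents without an arm limit, so this is not shown.

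**Conclusion.** The point holds for the grade limit. Taken literally, both endpoints classify a patient whose only severe event is fatal as event-free, and the separate death and SAE outputs do not amend the proportion. The size is about 1.3 to 1.4 points per such patient, on the assumption that the Safety population is near 78 and 71. The number of patients is not given and may be zero. No power loss and no effect on a planned test is claimed. The case for acting rests on the definition, not on a demonstrated distortion.

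Unequal contact after radiation is a caveat only. Arm A typically has 3 or 4 dosing visits in weeks 7-8, sometimes fewer in the exact 14 days after radiation, against no Arm B study visit in those weeks. A reader might infer biased toxicity rates from this, but the documents support only unequal contact.

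**What to change.** 1. Report both adverse event endpoints as grade 3 or higher (grades 3 to 5) in the Safety population, with the prespecified grade 3-4 proportion beside each. State that the broader definition was added after the interim analyses of December 2021 and March 2022 (SAP 8.3.1 and 8.3.2) in an open-label trial. If no patient had a fatal event only, say so, and the two figures will agree.
2. Optionally, add a supportive analysis of the any-event endpoint cut at each patient's last radiation date, with the prespecified window kept as the main analysis. State that the cut drops Arm A's last BMX-001 weeks and does not equalise contact during radiation.
3. Reconcile Protocol Table 4 footnote q and Protocol 13.3 with Table 4 footnote d, Protocol 9.1.7 and Protocol 13.8.2 on what contact Arm B had in weeks 7 and 8.

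The cost is a disclosed addition to a secondary endpoint, one extra line per endpoint and, if wanted, one sensitivity analysis. It needs no new data and no change to treatment or visits.

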### 9.1.2 Phase 2 Specific Design

The Phase 2 portion of this study will be a randomized, multi-center study comparing Arms A and B. Arm A will consist of daily TMZ and RT with BMX-001 and Arm B will include daily TMZ and RT alone.

For the Phase 2 Study, BMX-001 will be administered subcutaneously as a loading dose before starting concurrent chemoradiation (days -5 through 0 depending on patient/MRI scheduling), during treatment, and after treatment concludes. After the loading dose, the subsequent doses will be given two times per week for 8 weeks. The BMX-001 doses other than the loading dose will be delivered within 12 hours before or after RT. Patients will be randomized with a treatment arm allocation ratio of 1:1 to receive BMX-001 or to proceed with RT and TMZ alone. There will be 160 patients enrolled in this phase of the study (80 subjects per arm). The Phase 1 trial has confirmed the safe RP2D for BMX-001. The loading dose determined safe from Phase 1 and being studied in Phase 2 is 28 mg/subject and the maintenance doses are each 14 mg/subject.

BMX-001 will be administered by subcutaneous injection of a sterile 10 mg/mL solution in saline. The subcutaneous injections may be at any optimum site on the torso, the upper leg or upper arm. The first subsequent dose should be delivered 1 to 5 days after the loading dose and subsequent doses delivered at 3 to 4 day intervals to average 2 doses per week. The Phase 2 criteria for holding, retreating and discontinuing BMX-001 is captured in Section 13.4 BMX-001 Treatment Criteria.

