### 9.1.5 Missed Doses

Regardless of the reason for withholding study drug treatment, the maximum allowable length of treatment interruption is 3 weeks. If BMX-001 is withheld for greater than 3 weeks, BMX-001 will be discontinued. If BMX-001 is discontinued for missed doses, the patient will remain on the study and all planned study endpoints will be assessed. Any missed doses should be made up at the end of treatment, so that the subjects complete the planned number of doses (which is 17). Any missed doses of BMX-001 should be documented with the reason included.

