## **13.3** Chemoradiation Treatment Period (with and without BMX-001)

The treatment period for BMX-001 is eight weeks. This consists of treatment prior to start of chemotherapy- RT, during the six weeks of concurrent daily TMZ and standard RT with BMX-001 (Phase 1 and Phase 2 (Arm A)) followed by 2 weeks of BMX-001 (Phase 1 and Phase 2 (Arm A)). For subjects in Arm B, this period is six weeks of concurrent daily TMZ with standard RT followed by 2 weeks of no treatment. For subjects in Arm B, they do not need to return to the clinical center for a study visit once TMZ and RT is complete for visits at Week 7 and Week 8.

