11.2 METHOD OF SUMMARIZATION AND ANALYSIS

11.2.1 ADVERSE EVENTS DURING CHEMORADIATION

Each participating institution coded adverse events with their preferred term and organ class using MedDRA system organ class. Whether or not the adverse event was related to BMX-001 was determined for each event.

The initial summary of adverse events will consider all Treatment Emergent AE (TEAE) occurring during chemoradiation regardless of attribution to BMX-001. A TEAE is an event emerging during treatment having been absent pre-treatment or having worsened relative to pre-treatment. The period of observation that will be the focus of this tabulation will extend 2 weeks after termination of radiation treatment.

The population for these summaries will be the safety population as defined in Section 6.

For each study arm, the number of subjects with at minimum one Treatment Emergent AE (TEAE) will be tabulated by preferred term and MedDRA system organ class. Subjects with more than one TEAE will be counted only once, at casualty, for each system organ class /preferred term. Multiple TEAEs in a subject will be counted once per system organ class and preferred term. Summaries will be sorted by system organ class and decreasing total incidence of preferred term.

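### The window for BMX-001-related grade 3-4 events is tied to the end of radiation, so it closes about when planned dosing ends and usually before the last dose when make-up dosing runs late

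*SAP*

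**What the plan says.** SAP 11.1 defines two adverse event endpoints. Endpoint (1) is the proportion of patients with any grade 3 or 4 event during radiation and temozolomide. Endpoint (2) is the proportion with a grade 3 or 4 event "related to BMX-001 treatment during this same period". The section then fixes the window: "Adverse events occurring between baseline through 2 weeks after discontinuation of radiation will be the focus of these analyses and will be summarized". Protocol 16.5.2.3 has the same two endpoints and the same window. SAP 11.2.1 applies it to the treatment-emergent tables: "The period of observation that will be the focus of this tabulation will extend 2 weeks after termination of radiation treatment". SAP 11.2.3, the table of BMX-001-related events in Arm A, restates no cut-off, but its heading confines it to the chemoradiation period. Protocol Table 2 gives the related-event endpoint with no time window.

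On dosing, Protocol 9.1.2 says: "After the loading dose, the subsequent doses will be given two times per week for 8 weeks". Protocol 13.3 describes six weeks of chemoradiation with BMX-001 "followed by 2 weeks of BMX-001". Protocol 9.1.5 adds: "Any missed doses should be made up at the end of treatment, so that the subjects complete the planned number of doses". That number is 17, and a single interruption may last up to 3 weeks.

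On collection, Protocol 14.1 records events in Arm A "through 30 days after completion of the final BMX-001 treatment". SAP 11 agrees: "The collection of adverse events was stopped 30 days after completion of chemoradiation treatment +/- BMX-001".

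**The concern.** Endpoint (2) is meant to measure the toxicity of BMX-001, but its window is anchored to radiation. By the plan's nominal weeks, dosing and the window end together, two weeks after radiation, so the last doses get little follow-up inside the endpoint. Doses made up at the end move the last dose later and leave the window where it was. Some BMX-001 can then be given after the window has closed.

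At stake is the pre-specified rate of related grade 3-4 events, one of the figures that a decision on further development would use. A patient whose first such event comes after the window is recorded in the database but is not a case for the endpoint.

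**Working it through.** **Dose count.** One loading dose plus 2 per week x 8 weeks = 1 + 16 = 17, as in Protocol 9.1.5. The SAP's figure of 13 doses at 6 weeks also reproduces: 1 + 2 x 6 = 13.

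**Inputs to the timeline.**
- Radiation: 30 to 33 weekday fractions (Protocol 9.1.8.1). Day 1 is the first fraction, on any weekday.
- Loading dose: 0 to 5 days before radiation, on a weekday. Protocol 9.1.2 gives days -5 to 0; SAP 4 gives 0 to 4 days before. The two must be reconciled. The range used covers both.
- Maintenance: first dose 1 to 5 days after loading (Protocol 9.1.2), then 16 doses on Monday/Thursday or Tuesday/Friday. Those weekdays come from the Phase 1 text (Protocol 9.1.1.1) and are assumed for Phase 2.
- Window close = day of last fraction + 14.
- Gap = window close - day of last dose. A negative gap means that the window closes first.

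**On-time dosing.** These rules give 42 feasible schedules for each radiation length. The last dose falls on day 50 to 57.
- 30 fractions: radiation ends on day 40 or 42, so the window closes on day 54 or 56.
- 33 fractions: radiation ends on day 45 or 47, so the window closes on day 59 or 61.

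Example of the earliest close relative to dosing: Monday start, 30 fractions, loading on day 1, Monday/Thursday injections. The first maintenance dose is on day 4 and the sixteenth on day 57. The window closes on day 40 + 14 = 54, so the gap is 54 - 57 = -3 days.

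**Delayed completion.** A delay of d days lowers every gap by d.

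| Delay (days) | Gap, 30 fractions | Closes on or before last dose | Gap, 33 fractions | Closes on or before last dose |
|---|---|---|---|---|
| 0 | -3 to +6 | 12 of 42 | +2 to +11 | 0 of 42 |
| 7 | -10 to -1 | 42 of 42 | -5 to +4 | 32 of 42 |
| 14 | -17 to -8 | 42 of 42 | -12 to -3 | 42 of 42 |
| 21 | -24 to -15 | 42 of 42 | -19 to -10 | 42 of 42 |

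**Doses after the window in the worst case.** One full interruption with every dose made up: 3 weeks x 2 = 6 doses, and 6/17 = 35%. Counted schedule by schedule, 5 to 7 doses fall after the close with 30 fractions and 3 to 6 with 33.

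**Collected time that is not used.** Collection ends 30 days after the last dose, so the time between window close and end of collection is 30 - gap. With on-time dosing this is 30 - 6 = 24 to 30 + 3 = 33 days for 30 fractions, and 30 - 11 = 19 to 30 - 2 = 28 days for 33 fractions.

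**Direction.** A related event cannot precede the first BMX-001 dose. Extending the window to 30 days after the last dose can therefore only add patients to the numerator. Any error is an under-count. The documents do not say how many patients had made-up doses or late first events, so its size cannot be computed and could be zero.

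**The case against.** The window looks deliberate. Protocol 16.5.2.2 describes BMX-001 administration as continuing two weeks beyond radiation, so the cut-off was matched to planned dosing, and one common window serves the between-arm endpoint. A longer window runs into adjuvant temozolomide and leans harder on open-label attribution. These points stand. They support keeping the window for endpoint (1) and as a second display for endpoint (2).

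A reader might infer that late toxicity disappears from the report. The documents do not support that. The SAP calls the window a focus, says in 11.2.4 that all events will be listed, and plans an all-event summary in Section 19, where the table of related events carries no stated time limit. Protocol 16.5.2.3 adds adjuvant-phase tabulations for the monitoring board. SAP 11.2.3 could also be read as covering the whole BMX-001 period, since Protocol 13.3 places BMX-001 dosing within its chemoradiation treatment period. None of these outputs, however, yields the pre-specified proportion with related grade 3-4 events beyond the cut-off.

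A reader might also infer a demonstrated downward bias. That too goes beyond the documents. A patient whose dosing was held for a related grade 3-4 event inside the window is already a case, so events at that patient's made-up doses change nothing. Many of the effects listed in Protocol 5.6.2 are local or short-lived. This narrows the possible under-count but does not remove it. Protocol 13.4.1 also holds BMX-001 for events that need not make the patient a case, such as intolerable grade 2 injection site reactions and grade 2 QTc prolongation, and doses can be missed for other reasons.

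**Conclusion.** The concern holds in limited form. The endpoint (2) window is anchored to radiation and closes roughly 3 days before to 11 days after the last on-time dose. Once completion slips by about one to two weeks or more, it usually closes before the last dose. Related grade 3-4 events that first occur later are collected but not counted, so the endpoint can under-count related toxicity by an unknown amount.

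Two stronger statements would be wrong. The window does not generally close at or before the last dose: with on-time dosing it does so in 12 of 42 schedules at 30 fractions and in none at 33. Made-up doses are not always without follow-up: with a 7-day delay and 33 fractions, 10 of 42 schedules still close after the last dose. The figure of 6 in 17 doses is a worst case for one interruption, not an expected rate.

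The day counts rest on the assumed Phase 2 injection weekdays and on the loading-dose range. The schedule counts show what the rules allow; they are not patient frequencies. Separately, Protocol Table 2 and SAP 11.1 define the same endpoint differently. This is a cheap improvement to a secondary safety endpoint and does not touch the primary analysis.

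**What to change.** In SAP 11.1, define endpoint (2) as the proportion of Arm A patients with a BMX-001-related grade 3-4 event from the first BMX-001 dose to 30 days after the last. Give the SAP 11.2.3 table the same window, and align Protocol Table 2 and 16.5.2.3. SAP 11.2.3 says that related events can occur only in Arm A, so no between-arm comparison is disturbed.

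Leave endpoint (1) on the window ending two weeks after radiation. It needs a period common to both arms, because Arm B collection ends 30 days after chemoradiation. Show endpoint (2) on that window as a secondary display, so that the effect of the change is visible.

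With this definition the window would close on day 50 + 30 = 80 to day 57 + 30 = 87 with on-time dosing, and on day 101 to 108 with a 21-day delay.

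The cost is a wording change and one extra display; the data are already collected. The downside is overlap with adjuvant temozolomide, which can start up to 4 weeks after radiation (Protocol Table 4, note b). On the nominal weeks, the extended window ends about 14 + 30 = 44 days after radiation, so the overlap is at least about 44 - 28 = 16 days for patients who start by then. Attribution in that stretch is an open-label judgement and should be reported as such. The amendment should be dated before the related-event tables are run.
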